STUDY PROTOCOL

Principal Investigator: [name]

[contact]

E-mail: [contact]

Protocol Date: 12/21/2020

ClinicalTrials.gov number: NCT04617496

1. Aims/Objectives

The great majority of individuals with Parkinson's disease (PD) develop speech impairments (Ho et al., 1999; Miller et al., 2007; Schalling et al., 2017), most of which are grouped together and called hypokinetic dysarthria. Hypokinetic dysarthria is typically characterized by altered prosody (e.g., reduced loudness and pitch variation), phonation (e.g., breathy or harsh voice), and articulation (e.g., imprecise consonants, centralized vowels) (Fox & Ramig, 1997; Ho et al., 1999; Hillenbrand & Houde, 1996). Changes in speech may appear early in PD (Miller et al., 2008; Rusz et al., 2011; Skodda et al., 2013) and progress in severity over time (Skodda et al., 2013; Skodda et al., 2009; Skodda, Flasskamp, et al., 2011). Further, such changes in speech lead to significant declines in functional communication and quality of life (Miller et al., 2006 & 2007). Pharmacological and surgical interventions that alleviate motor symptoms in PD are largely ineffective or sometimes even detrimental for speech (Ho et al., 2008; Schulz & Grant, 2000). We propose a pilot randomized, controlled trial (RCT) in patients with hypokinetic dysarthria in PD to assess the potential effectiveness of a home-based exercise intervention with interactive automated speech response features that encourage a higher level of speech performance. The overall goal of this project is to determine if this intervention leads to improved global speech function. The results of this project will provide important information that can be used to design a definitive future trial. Our Specific Aims are:

Primary Aim

Specific Aim 1: To determine whether there is a difference in change in speech intelligibility (how well an individual is understood by others) between patients randomized to the intervention program vs. patients randomized to the health education control program.

Hypothesis: Patients in the intervention program will improve in speech intelligibility at 6 months, as compared with patients in the health education control program.

Secondary Aim

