Specific Aim 2: To determine whether there is a difference in change in self-perceived communication ability (measured via the Communication Effectiveness Index) between patients randomized to the intervention program vs. patients randomized to a health education control program.

Hypothesis: Patients in the intervention program will improve in the Communication Effectiveness Index at 6 months, as compared with patients in the health education control program.

2. Background Information

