7.2 Communication Effectiveness Index

Research indicates that the impact of hypokinetic dysarthria in PD goes beyond severity of speech impairment; it reduces the patient's ability to effectively communicate in daily life (Miller et al., 2008; Miller et al., 2006; McNamara & Durso, 2003). In the proposed study, we will measure the Modified Communication Effectiveness Index (CETI-M), a comprehensive patient-reported outcome. Specifically, participants will rate their communicative effectiveness in 10 different speaking situations (e.g., in noisy environments, over the phone) on a 10-point Likert scale, where 1 = not effective and 10 = extremely effective.

8. Statistical Analysis Plan

Primary Aim

Specific Aim 1: Our primary outcome will be the change in speech intelligibility at 6 months. Because each individual contributes up to two values, at baseline and at 6 months, PROC MIXED (SAS) will be used to estimate regression parameters based on a mixed-effects longitudinal model (Diggle et al., 1994) with the use of the REPEATED statement with an unstructured covariance matrix.

Secondary Aim

Specific Aim 2: We will perform univariate analyses based on the Mann-Whitney U test to compare the distribution of change in CETI-M scores from baseline to 6 months in the intervention vs. control group.

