8.1 Power

With the use of a randomized pre-post LSVT design in patients with hypokinetic dysarthria in PD, Cannito et al. (2012) observed an effect size of 0.75 for the outcome speech intelligibility treated as a continuous variable (our primary outcome). With a sample size of 39 participants per group, we will have 90% power ($\alpha=0.05$) to detect this effect size.

9. References

Bradlow A, Torretta G, Pisoni D. Intelligibility of normal speech I: Global and fine-grained acoustic phonetic

talker characteristics. *Speech Commun.* 1996;20:255–272.

Darkins A. The growth of telehealth services in the Veterans Health Administration between 1994 and 2014: A study in the diffusion of innovation. *Telemed J E Health.* 2014;20:761-8.

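### Aim 2's unadjusted Mann-Whitney test on CETI-M change is valid, but at low to moderate baseline-to-6-month correlation it has less power than a baseline-adjusted analysis

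*Combined protocol and SAP*

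**What the plan says.** Section 8 (Secondary Aim, Specific Aim 2) plans "univariate analyses based on the Mann-Whitney U test to compare the distribution of change in CETI-M scores from baseline to 6 months", intervention against control. It names no covariate, adjusted follow-up analysis, effect estimate or confidence interval for this aim.

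Section 7.2 describes the instrument: "participants will rate their communicative effectiveness in 10 different speaking situations", each "on a 10-point Likert scale, where 1 = not effective and 10 = extremely effective". It does not say how the ten ratings become one score.

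Section 1 (Secondary Aim) asks "whether there is a difference in change in self-perceived communication ability", with the hypothesis that "Patients in the intervention program will improve in the Communication Effectiveness Index at 6 months" relative to control.

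For Aim 1, by contrast, section 8 says that PROC MIXED "will be used to estimate regression parameters based on a mixed-effects longitudinal model". Section 8.1 states "With a sample size of 39 participants per group, we will have 90% power", but for speech intelligibility only. Section 1 presents the trial as a pilot whose results should "provide important information that can be used to design a definitive future trial".

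**The concern.** Baseline CETI-M is collected on every patient but used only to form a difference. A change score gives the baseline a fixed weight of one. If baseline and 6-month scores are only moderately correlated, that weight is too large, and subtraction adds baseline noise to the outcome. A model with baseline as a covariate estimates the weight from the data.

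CETI-M is the only secondary aim and the only patient-reported outcome, and no power is stated for it. Avoidable loss of power makes a real benefit easier to miss. A Mann-Whitney p-value alone also gives the planners of a definitive trial no effect size and no SD.

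**Working it through.** **1. The plan's own figure.** Section 8.1 gives 39 per group, effect size 0.75 and alpha 0.05. By the normal approximation, 0.75/√(2/39) = 0.75/0.2265 = 3.312; 3.312 − 1.960 = 1.352; power 91.2%. The noncentral t gives 90.5%. The stated 90% reproduces two-sided, but it does not concern CETI-M.

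**2. Inputs for CETI-M.** From the documents: the test, ten items scored 1-10, the 6-month time point, 104 randomised 1:1. I take 39 per arm as the number analysed; 2 × 39 = 78 is 75% of 104, although the plan does not call the difference a loss allowance. Assumed, because the documents give nothing: true effect 0.5 SD, equal SDs at both visits, rho 0.3 to 0.8, two-sided 5%, complete data.

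**3. Formulas (normal data, SD = 1).**
- Variance of the difference in mean change: (2/n) × 2(1 − rho)
- Variance of the ANCOVA estimate: (2/n) × (1 − rho²)
- Ratio, ANCOVA to change: (1 + rho)/2 = 0.65, 0.75, 0.85, 0.90 at rho 0.3, 0.5, 0.7, 0.8
- Mann-Whitney has a further efficiency factor of 3/π = 0.955 under normality
- Power ≈ Φ(effect/SE − 1.960)

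At rho 0.5 the change-score SE is √(2/39 × 1) = 0.2265. Mann-Whitney: 0.5/0.2265 × √0.955 = 2.157, power 57.8%. The ANCOVA SE is √(2/39 × 0.75) = 0.1961; 0.5/0.1961 = 2.550, power 72.2%. Over the four values of rho, Mann-Whitney has 44.6/57.8/79.5/92.7% and ANCOVA 63.9/72.2/87.1/95.7%. With a 0.35 SD effect at rho 0.5, the same steps give 0.35/0.2265 × √0.955 = 1.510 (32.6%) and 0.35/0.1961 = 1.785 (43.0%), a gain of about 10 points.

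**4. Simulation.** 10,000 replicates per cell, simulation SE at most 0.5 point. Cells show Mann-Whitney / ANCOVA power in %, with ANCOVA's gain in points.

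| Setting | rho 0.3 | rho 0.5 | rho 0.7 | rho 0.8 |
|---|---|---|---|---|
| Normal | 43.1 / 63.5 (+20) | 56.4 / 70.3 (+14) | 76.8 / 85.4 (+9) | 92.1 / 95.1 (+3) |
| Ten 1-10 items near ceiling, normal noise | 33.3 / 53.6 (+20) | 42.1 / 59.4 (+17) | 55.1 / 70.0 (+15) | 66.6 / 78.5 (+12) |
| Ten items near ceiling, t3 noise | 46.4 / 61.7 (+15) | 54.6 / 64.9 (+10) | 66.4 / 74.1 (+8) | 74.7 / 81.4 (+7) |
| Ten items mid-scale, t3 noise | 51.0 / 65.8 (+15) | 60.7 / 70.7 (+10) | 73.1 / 78.8 (+6) | 81.7 / 85.6 (+4) |
| Unbounded t3 noise | 62.1 / 66.9 (+5) | 77.1 / 74.5 (−3) | 93.3 / 88.2 (−5) | 98.7 / 95.2 (−4) |

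Item rows: latent mean 8 (near ceiling) or 5.5 (mid-scale), latent SD 1.8, item SD 2, rounded and clipped to 1-10, then averaged. There rho is latent; near the ceiling with normal noise the observed correlations are 0.26/0.43/0.61/0.70.

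**5. How much is due to adjustment?** Rank ANCOVA keeps ranks and adds baseline. On normal data its power is 60.5/67.0/81.7/92.1%, a gain over Mann-Whitney of 17/11/5/0 points. At rho 0.8 the whole 3-point ANCOVA gain therefore comes from leaving ranks.

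**6. Sensitivity to item noise.** Item SD 2 is an assumption, and normal item noise dilutes heavy tails. With t3 noise, mid-scale items, latent SD 1.8 and 4,000 replicates:
- Item SD 1, Mann-Whitney / ANCOVA: 72 / 78% at rho 0.5, 87 / 88% at 0.7, 95 / 94% at 0.8
- Item SD 0.5: 74 / 78%, 92 / 91% and 98 / 96%

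With latent SD 1 and item SD 0.5, Mann-Whitney leads by 2 to 3 points at 0.7 to 0.8. One-point differences are close to simulation error: √(0.91 × 0.09/4000) is about 0.5 point per estimate. At rho 0.5 ANCOVA led by 2 to 7 points in all these bounded runs.

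**7. Validity.** Null rejection in the 10,000-replicate runs was 4.4 to 5.5% over all tests and settings.

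**8. No loss to follow-up (52 per arm).** Normal: 55/69/89/97% against 75/83/94/99%. Items near the ceiling: 43/53/69/80% against 67/72/82/89%.

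**The case against.** The strongest defence is that nothing is broken. The planned test holds its level, and it addresses the difference in change that Aim 2 asks about. A rank test on a summary of Likert ratings is a reasonable choice, and it protects against outliers. The outcome is secondary and the trial a pilot. All of this stands, and it limits the point to efficiency.

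It is also fair that the size cannot be fixed from the documents. On normal data the gain falls from 20 points to 3 as rho rises from 0.3 to 0.8, and the documents do not say which rho applies.

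A reader might infer that a scale bounded at 1 and 10 rules out the heavy-tailed case, so that ANCOVA must win at every rho. The documents do not support this. They give no item variability, and with small item noise the planned test draws level or slightly ahead at rho 0.7 to 0.8 on the bounded scale too.

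A reader might also infer from the Aim 1 model that Aim 2 needs one as well. Aim 1 shows only that a model for a bounded outcome is not foreign to this plan; it does not show that a rank test is wrong for ratings.

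The objection does not remove the gain at rho 0.5 or below. ANCOVA led there in every normal and bounded-scale run. With unbounded t3 noise it led at 0.3 and trailed by about 3 points at 0.5.

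**Conclusion.** The point holds as a recommended improvement, with medium confidence. At low to moderate correlation the planned test gives up roughly 14 to 20 points of power on normal or ceiling-affected scores, with 39 per arm and a 0.5 SD effect. At rho 0.7 to 0.8 the gain from ANCOVA is 3 to 9 points for normal data and 12 to 15 near the ceiling with item SD 2. With heavy-tailed noise the gain is smaller and can reverse at those correlations: by about 4 to 5 points if unbounded, and by about 1 to 3 on a bounded mid-scale instrument with small item noise. Every figure rests on the assumed effect, SDs, correlation and item model.

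Three stronger readings should be resisted. The planned test is not biased or invalid. The documents do not show that Aim 2 is underpowered, because they set no target effect for CETI-M. Nor should the precision gain be overstated. In simulation with normal data the ratio of the ANCOVA SE to the change-score SE is 0.811/0.871/0.928/0.955, a confidence interval about 19/13/7/5% narrower. That comparison is with an unadjusted mean difference in change, which the plan does not propose, and not with the Hodges-Lehmann interval that pairs with the planned test.

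**What to change.** In section 8, make the main Aim 2 analysis an ANCOVA of 6-month CETI-M on baseline CETI-M and group. Report the adjusted mean difference with its 95% CI, and the SD. Keep the Mann-Whitney test on change, with the Hodges-Lehmann shift and its CI, as the prespecified sensitivity analysis.

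The aim's question is preserved. If change = a + b × baseline + c × group, then the 6-month score = a + (b + 1) × baseline + c × group, so the group coefficient c is the same for either outcome. The patients are also the same: those with both scores.

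The cost is SAP wording, with no new data. The downsides are some reliance on approximately normal residuals for a bounded score, and a small loss of power if change is heavy-tailed and rho is high; the retained Mann-Whitney analysis covers that case. ANCOVA's simulated null rejection was 4.8 to 5.3% with bounded items and 4.4 to 5.0% with unbounded t3 noise. Rank ANCOVA is an alternative, but at very high rho it can be weaker than the planned test (normal data, rho 0.9, 0.25 SD effect: 62.4% against 66.4%).

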8.1 Power

With the use of a randomized pre-post LSVT design in patients with hypokinetic dysarthria in PD, Cannito et al. (2012) observed an effect size of 0.75 for the outcome speech intelligibility treated as a continuous variable (our primary outcome). With a sample size of 39 participants per group, we will have 90% power ($\alpha=0.05$) to detect this effect size.

9. References

Bradlow A, Torretta G, Pisoni D. Intelligibility of normal speech I: Global and fine-grained acoustic phonetic

talker characteristics. *Speech Commun.* 1996;20:255–272.

Darkins A. The growth of telehealth services in the Veterans Health Administration between 1994 and 2014: A study in the diffusion of innovation. *Telemed J E Health.* 2014;20:761-8.

